### **D. Definition of Primary and Secondary Outcomes/Endpoints**

Generally, primary safety analyses will be based on time from baseline or 30 days after baseline until two months after patients first reached direct bilirubin levels  $< 2$  mg/dL. Baseline will be defined as information collected at the date that treatment starts for Omegaven® patients and on the date that patient reached bilirubin levels  $> 2$  for soybean oil fat emulsion patients. Information on mortality and transplant will be collected during the whole treatment with Omegaven®. Primary efficacy analysis will include time from baseline until the patient normalizes bilirubin (presents three consecutive direct bilirubin  $\leq 2$  mg/dL or a direct bilirubin  $\leq 2$  mg/dL and weaned from TPN).

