### Outcome/Endpoints

#### *Treatment safety*

Our primary outcome for treatment safety will be based on patient's essential fatty acid profile. We will compare patients before treatment with Omegaven® started and after treatment started (one month after treatment started until treatment stopped) with respect to the frequency with which triene/tetraene ratio  $> 0.2$  at any time. Primary analyses for these and all other safety outcomes will be based on a follow-up time for Omegaven® starting 30 days after baseline, i.e., 30 days after treatment started for Omegaven® patients and 2 months after the first direct bilirubin level  $< 2$  mg/dL was recorded.

Additional comparisons across treatment periods for subjects receiving Omegaven® will be aimed to assess occurrence of spontaneous bleeding (e.g., unexplained bruising, oozing from gums/incision sites), and maximum triene/tetraene ratio, minimum platelets, maximum international normalized ratio (INR), and trends in pre-albumin (age standardized levels). We will also explore trends in coagulopathies based on curves of platelets, prothrombin time (PT), partial thromboplastin time (PTT) over time, and INR. We will also describe the rate with which INR ratios were  $> 2$  (number of days/follow-up time), as a marker of coagulopathies.

Additional evaluation of Omegaven® will be performed with regards to rate in which albumin is  $> 3$  g/dL, maximum triglyceride level, rate of blood stream infections (number of positive blood cultures/follow-up-time under PN after baseline), rate of central venous catheter (CVC) infections (number of CVC infections/follow-up time and number of gram positive CVC infections/follow-up time), and occurrence of anaphylactic reactions after baseline.

We will describe trends over time for all outcomes associated with fatty acid profiles (including triene/tetraene ratios, triglycerides, total omega-6 fatty acids, total omega-3 fatty acids, total saturated, total monounsaturated, and total polysaturated fatty acids). Specific fatty acids such as arachidonic, palmoleic, palmitic, oleic, stearic, and linoleic fatty acids will also be evaluated and described.

[name], Department of Surgery, Children's Hospital & Medical Center  
[name], Department of Surgery, Children's Hospital & Medical Center  
[name], Pediatric Research Office, Dept. of Pediatrics, UNMC  
[name], Department of Biostatistics, College of Public Health, UNMC

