### *Analysis of Safety and Tolerability of Omegaven®*

All primary safety and tolerability analyses will be based on descriptive statistics. In secondary analyses, we will also assess the statistical significance of differences. The period receiving Omegaven® will start 30 days after beginning PN with Omegaven® for the main analysis. Outcomes measured in the Omegaven® will be described for a period starting 30 days after baseline.

Primary outcomes measured will include whether the triene/tetraene ratio was ever  $> 0.2$  during the intervention period and whether the INR was ever  $> 2$ . Secondary outcomes measured will include platelets, prothrombin time (PT), partial thromboplastin time (PTT), and other components of the fatty acid profile. Analysis of all categorical outcomes will be based on proportions and of all continuous outcomes will be based on means or medians of the individual mean, maximum or minimum values, as appropriate, during the respective follow-up period. Comparisons between periods (pre and post-treatment) will be performed based on paired tests, parametric or non-parametric, as appropriate. We will also explore trends over time (e.g., decreasing for INR and increasing for pre-albumin) and estimate p-values via regression models using generalized estimating equations or random effects to account for within subject correlations. When describing outcomes over time, we will explore the effect of predictors of poor hepatic outcomes, such as use of antifungal agents (e.g., amphotericin) and antidiarrheal agents (e.g., loperamide), on potential spikes.

[name], Department of Surgery, Children's Hospital & Medical Center  
[name], Department of Surgery, Children's Hospital & Medical Center  
[name], Pediatric Research Office, Dept. of Pediatrics, UNMC  
[name], Department of Biostatistics, College of Public Health, UNMC

We will also evaluate nutritional outcomes including difference in weight-for- age Z-scores and height-for-age Z-scores from baseline to the moment in which the child starts enteral feeding and to the moment in which the child receives less than 10% of their calories from PN. Using linear regression, we will explore adjustment for baseline alternative predictors of interest. Trends over time in Z-scores will also be explored using regression with repeated measure methods.

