#### **Safety Labs Schedule:**

Lab Name	Schedule*
Serum triglycerides	At baseline, weekly for 4 weeks, monthly thereafter
Coagulation labs	At baseline, weekly until direct bilirubin is < 2mg/dL, monthly thereafter
Fatty acid profile	At baseline, monthly thereafter

\*minimum requirements, may be performed more frequently for routine clinical care

If under the discretion of the principal investigator the patient is able to return home and receive Omegaven®, the patient is required to return to Children's Hospital & Medical Center every 2 months or other mutually agreed upon schedule for evaluation and follow up. The Principle Investigator also requires for arrangements to be made through the patient's home health care agency for the required weekly or monthly blood draws the patient will need while at home in order to remain on Omegaven®. The lab results then must be faxed to Children's Hospital & Medical Center in a timely manner. Additionally, measures will be taken to decrease the chance of administration errors when Omegaven® is given in the home. Families will be provided with a letter outlining strategies for reducing medication administration errors, such as independent double-checks.

Dose reduction will occur if there is evidence of lipid intolerance (serum triglycerides  $>$  200mg/dL) or evidence of bleeding. Growth indices include weight, length, and head circumference will also be monitored.

Other standard care laboratory results will be captured for the Omegaven® protocol. These are listed along with the standard schedule in Table 3.

The frequency of laboratory monitoring may be reduced to monthly or as clinically necessary, for patients who have been on a stable regimen of Omegaven® for a minimum of 4 months and whose serum bilirubin and hepatic enzymes have normalized.

The study team will round on all inpatients receiving Omegaven® therapy. A complete comprehensive case review for all inpatients receiving Omegaven® therapy under the compassionate-use protocol and any outpatients issues will be discussed among [name], [name], and the study coordinator. All pertinent medical, nutritional, and psychosocial outpatient information will be reviewed during these case reviews.

[name], Department of Surgery, Children's Hospital & Medical Center  
[name], Department of Surgery, Children's Hospital & Medical Center  
[name], Pediatric Research Office, Dept. of Pediatrics, UNMC  

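### The primary safety window opens at day 30 for all safety outcomes, so first-month INR > 2 and bleeding fall outside it, and the protocol gives conflicting ends for it

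*Protocol*

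**What the plan says.** **Start of the window.** Three places in the Protocol address it.

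- Treatment safety: "Primary analyses for these and all other safety outcomes will be based on a follow-up time for Omegaven® starting 30 days after baseline". This covers the triene/tetraene ratio and every other safety outcome.
- Analysis of Safety and Tolerability: "The period receiving Omegaven® will start 30 days after beginning PN with Omegaven® for the main analysis". The same section names two primary outcomes: the triene/tetraene ratio ever above 0.2 "during the intervention period and whether the INR was ever" above 2.
- Section D: "Generally, primary safety analyses will be based on time from baseline or 30 days after baseline until two months after patients first reached direct" bilirubin below 2 mg/dL. It does not say which outcomes start at baseline and which at day 30.

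One item is worded differently: "occurrence of anaphylactic reactions after baseline". The blood stream infection rate is likewise counted from baseline.

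**End of the window.** For the triene/tetraene ratio, Treatment safety gives "one month after treatment started until treatment stopped". The next sentence, on that ratio and all other safety outcomes, points to two months after the first direct bilirubin below 2 mg/dL, as section D does. The analysis section speaks only of an intervention period, with no date.

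**Sampling.** The Safety Labs Schedule sets minimum draws. Triglycerides: "At baseline, weekly for 4 weeks, monthly thereafter". Coagulation: "At baseline, weekly until direct bilirubin is < 2mg/dL, monthly thereafter".

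**The concern.** Safety is Aim 1, and hypothesis 1.2 names bleeding and coagulopathies. A lag is understandable for a fatty-acid profile, which takes time to shift after the emulsion is changed. The protocol gives no reason for applying the same lag to INR, bleeding, platelets or triglycerides, for which the first weeks of exposure matter too.

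The primary safety analysis is descriptive, so the reported proportions are themselves the result. A patient whose INR exceeds 2 only in the first month would not count towards a primary outcome. INR above 2.0 is also a listed example of toxicity for which the Principal Investigator may withdraw a patient. A patient withdrawn for it before day 30 adds no on-treatment data to the window.

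The end matters because treatment continues until weaning from PN, which may come long after bilirubin responds. Two analysts following the text could use different windows for the same primary outcome.

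**Working it through.** The protocol gives no figure for the effect of the window. The power values in Table 4 do not bear on it; only its sample sizes (20, 25, 30) are used below.

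**1. Start.** Treatment safety and the analysis section both fix day 30. Section D allows baseline or day 30. No text exempts INR, bleeding, platelets or triglycerides. Anaphylaxis and blood stream infection are read here as starting at baseline, from their wording.

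**2. End.** Treatment stop and response plus two months coincide only by chance. The second does not exist for a patient who never falls below 2 mg/dL.

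**3. Draws before day 30 (minimum schedule, baseline draw not counted).**

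- Triglycerides: days 7, 14, 21 and 28, so 4 draws.
- Coagulation: 4 if bilirubin stays at or above 2 through day 28; 2 if it falls below 2 at day 14; 0 if the patient enters below 2, which is possible for transfers already on the drug.

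The Reversal Study Lab Schedule and Table 3 continue lipid or triglyceride draws weekly while bilirubin is at or above 2. Weekly triglycerides are therefore confined to the first four weeks only under the minimum schedule.

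**4. Treated time excluded.** Response and stop days are assumptions. End A is treatment stop; end B is the earlier of stop and response + 60 days. Excluded share = 1 − (end − 30)/stop.

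| Response / stop day | End A | End B |
|---|---|---|
| 60 / 180 | 1 − 150/180 = 16.7% | 1 − 90/180 = 50.0% |
| 120 / 180 | 1 − 150/180 = 16.7% | 1 − 150/180 = 16.7% |
| 60 / 365 | 1 − 335/365 = 8.2% | 1 − 90/365 = 75.3% |

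For triene/tetraene in the 60/365 case, the monthly minimum gives 12 draws in the window under A (days 30 to 360) and 4 under B (days 30, 60, 90, 120). If the panel is drawn weekly until response, as the Reversal Study Lab Schedule has it, the counts are 14 and 6.

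**5. Effect on a reported proportion.** Assume 2 patients have INR > 2 only before day 30. For 0 events in n patients, the exact two-sided 95% upper limit is 1 − 0.025^(1/n).

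| Whole period | Day-30 window, both stay | Day-30 window, both withdrawn |
|---|---|---|
| 2/20 = 10.0% | 0/20, upper limit 16.8% | 0/18, upper limit 18.5% |
| 2/25 = 8.0% | 0/25, upper limit 13.7% | 0/23, upper limit 14.8% |
| 2/30 = 6.7% | 0/30, upper limit 11.6% | 0/28, upper limit 12.3% |

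**6. Direction.** For a patient kept in the denominator, removing days 0–30 only removes observations. An *ever* outcome or a maximum cannot rise, and a minimum cannot fall. If early leavers drop out, the direction is not fixed. With 2 late events in 20 patients and 2 event-free early exits, 2/20 = 10.0% becomes 2/18 = 11.1%.

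**The case against.** The strongest defence is that nothing is hidden. Adverse events are reported from the first infusion, withdrawn patients have their measurements recorded up to withdrawal, the DSMB reviews safety data, and death and transplant are collected throughout treatment. This stands. A reader might infer that first-month events are lost to the study; the documents do not support that. The gap is in the defined analysis, not in surveillance.

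A reader might also infer that the day-30 start can only flatter the drug. That holds for patients who remain in the denominator. It fails if event-free early leavers are dropped, as step 6 shows. Requiring an expected further 30 days of PN at entry should make early exits uncommon, but does not rule them out.

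Nor are all the affected outcomes primary. INR ever above 2 is; bleeding, platelets and maximum triglycerides are additional or secondary.

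Early abnormal INR may reflect liver disease at entry rather than the drug. That is a plausible reason for a lag, but the protocol does not state it, and a separate row for days 0–30 would show such values instead of omitting them.

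Finally, ending at treatment stop lengthens only the on-treatment side of the before/after comparison, which tends to raise *ever* proportions. This objection is fair and qualifies the remedy.

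**Conclusion.** The point holds and should be fixed. The plan fixes a day-30 start for all safety outcomes in two sections, leaves the start open in a third, and gives two incompatible ends for the same primary outcome, one of them undefined for non-responders. First-month INR > 2 therefore falls outside a primary result of Aim 1, and first-month bleeding, low platelets and high triglycerides fall outside their defined analyses.

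The part of the size that comes from the protocol itself is 4 triglyceride draws and up to 4 coagulation draws before day 30 on the minimum schedule. The rest depends on assumptions: 8% to 75% of treated time excluded across the assumed courses, and a 6.7% to 10.0% proportion reduced to zero when two patients have early events only. The documents give no expected early event rate, so they do not show that the safety result would in fact be misleading.

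**What to change.** Reconcile section D, Treatment safety and the safety analysis section as follows.

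- **Start:** the first infusion under this protocol for INR, bleeding, platelets, triglycerides and other non-fatty-acid outcomes. Keep the 30-day lag only for the triene/tetraene ratio and the fatty-acid components. Say explicitly that triglycerides are not lagged, since the protocol groups them with the fatty-acid outcomes when describing trends.
- **End:** one date, stated identically in all three places and defined for every patient. Treatment stop, already given in Treatment safety, meets this.
- **Denominator:** all treated patients, including those who leave before day 30.
- **Reporting:** show days 0–30 as a separate row and give follow-up time beside each *ever* proportion. State that before/after *ever* comparisons cover periods of unequal length, and report rates per follow-up time as well.
- **Sensitivity analysis:** day 30 to two months after bilirubin response, with a stated end for patients who never respond.

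The cost is wording and some rerun tables on data already collected, with no new visits or tests. Event rates may look less favourable, and follow-up will differ between patients and between periods.

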**Hypothesis for Aim 2:**

2.1 – Our primary hypothesis is that, after reaching bilirubin levels  $> 2$  mg/dL, patients receiving Omegaven® will reach a bilirubin level  $\leq 2$  mg/dL faster than patients receiving conventional fat emulsions. Additionally, while patients receiving Omegaven® will experience a decrease in their levels of bilirubin and other hepatic enzymes over time, patients receiving conventional emulsions will maintain high levels of bilirubin and other hepatic enzymes over time.

2.2 – Patients with surgical gastrointestinal disease and cholestasis will have better clinical hepatic outcomes than patients receiving conventional emulsions.

2.3 – Since patients receiving Omegaven® will have improved immune function, they will have a lower infection rate than patients receiving conventional fat emulsions.

2.4 – Due to a better general hepatic condition, patients receiving Omegaven® will also experience lower occurrence of liver transplant, death from hepatic associated causes, and blood transfusions.

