Assessment of efficacy will be also based on comparison of means (or medians) of the mean and maximum modified PELD scores of each subject across all follow-up weeks. Adjustments of these comparisons for potential confounders will be based on linear regression models. Mean rates of infection will be compared using logrank and Cox proportional hazards models.

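### The bloodstream infection rate is defined by counting positive blood cultures, so an infection with repeat positives is counted more than once

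*Protocol*

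**What the plan says.** In the Protocol, section D, under Treatment safety, the additional evaluations include a rate of bloodstream infections, defined as "number of positive blood cultures/follow-up-time under PN after baseline". The numerator is therefore positive cultures, and the denominator is time on parenteral nutrition (PN) after baseline. In the same sentence the catheter outcomes have infections as their numerator: "number of CVC infections/follow-up time and number of gram positive CVC infections/follow-up time".

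No section defines a bloodstream infection episode, sets a window for repeat positive cultures, or says how several positives with one organism are counted. The laboratory schedules in the Data and Safety Monitoring Plan and in Tables 2 and 3 contain no blood cultures, so the Protocol does not fix how often cultures are taken.

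The rate bears on hypothesis 2.3, which says of Omegaven patients that "they will have a lower infection rate than patients receiving conventional fat emulsions". On analysis, the safety section states that "All primary safety and tolerability analyses will be based on descriptive statistics" and adds that "In secondary analyses, we will also assess the statistical significance of differences". The efficacy section states that "Mean rates of infection will be compared using logrank and Cox proportional hazards models".

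**The concern.** The label and the numerator describe different things. A reader of the results will take a bloodstream infection rate to mean how often children became infected. The stated rule gives how often a culture came back positive. The two agree only if every infection yields exactly one positive culture, and nothing in the Protocol ensures that.

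Two things are at stake. First, the descriptive rate can overstate the infection burden. Secondly, it carries the effect of culture-taking practice. The study is non-randomized and open-label (section A), and cultures are taken outside any protocol schedule. The number of positives per infection may therefore differ between treatment periods, or between Omegaven patients and those on conventional emulsion, for reasons unrelated to infection risk. Such a difference would appear as a difference in infection rate.

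**Working it through.** **Inputs.** The numerator and denominator come from Treatment safety. The Protocol reports no infection count, rate or follow-up time, so there is no figure to reproduce and no absolute corrected rate can be computed. The mean number of positive cultures per episode, m, is not given. I assume a range of 1 to 4.

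**Step 1: effect on the rate.** Let E be the number of culture-proven episodes, T the PN follow-up time, and C the total number of positive cultures. Then m = C/E, and

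reported rate = C/T = m × (E/T).

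- m = 1: the episode rate is multiplied by 1.0 (no change)
- m = 1.5: by 1.5
- m = 2: by 2.0
- m = 3: by 3.0
- m = 4: by 4.0

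Each culture-proven episode has at least one positive culture, so m cannot fall below 1. Repeat positives can only push the rate up.

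**Step 2: sensitivity to one child.** The power section considers 20, 25 or 30 patients, so totals may be small. As an illustration with assumed counts, take ten episodes, nine with one positive culture and one with five. Then C = 9 × 1 + 1 × 5 = 14, and 14/10 = 1.4. One persistent infection raises the reported rate by 40%.

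**Step 3: effect on a comparison.** For groups or periods 1 and 0 with episode rates r1 and r0,

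reported rate ratio = (r1 × m1)/(r0 × m0).

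- If m1 = m0, the factor cancels and the ratio is unaffected, although both rates are inflated.
- If r1 = r0 but m1 = 2.0 and m0 = 1.5 (assumed), the ratio is 2.0/1.5 = 1.33 with no true difference.
- With those values exchanged it is 1.5/2.0 = 0.75, an apparent 25% reduction with no true difference.

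The size of m distorts the descriptive rate. A difference in m distorts a comparison.

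**The case against.** **Episode rules are often left to a statistical analysis plan.** The window and organism rule could well stand there, and the parenthesis might be meant only to say that infections must be culture-proven. That would answer a complaint about missing detail. Here, however, the Protocol states the numerator itself, and a later plan that followed it would count cultures. The objection reduces the weight of the point but does not remove it.

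**The size is assumed.** This stands. The Protocol gives neither m nor any culture practice, and at m = 1 nothing changes.

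**The bloodstream and catheter rates use different numerators.** A reader might call this a contradiction. It is not one: they are separately named outcomes, and the Protocol never combines or compares them. It only limits reading the two rates side by side.

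**Infection is also captured as an event.** The adverse event section lists bloodstream infection and re-hospitalization for it, so safety oversight does not rest on culture counts. That is true, but it does not redefine the rate.

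**The stronger reading: standard errors or intervals are too small.** A reader might infer this because positives within one infection are not independent. If cultures were analysed as independent Poisson events, the standard error would be too small by √m when m is fixed (1.41 at m = 2, 1.73 at m = 3). If cultures per episode followed 1 + Poisson(k), so that m = 1 + k, the variance-to-mean ratio would be (k + m²)/m. At m = 2 that is (1 + 4)/2 = 2.5, a factor of √2.5 = 1.58. But the Protocol names no interval, standard error or Poisson model for this rate. Primary safety analyses are descriptive, and comparisons between periods use paired tests. Trends over time use "regression models using generalized estimating equations or random effects to account for within subject correlations". The logrank and Cox comparison of infections, if based on time to first infection, is unaffected by repeat cultures. The documents therefore do not support a claim that planned error bars are wrong.

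**Conclusion.** The definition is wrong as written, and the point is minor. An outcome labelled as an infection rate is fixed as a culture rate with no rule for repeat positives, so the reported figure equals the episode rate times the mean number of positive cultures per episode. The direction is certain: upward or no change. The size is unknown, a factor of 1 to 4 over the assumed range. The effect on hypothesis 2.3 requires two further conditions: that cultures per episode differ between the periods or groups compared, and that the comparison uses the rate as defined and not time to first infection. The outcome is an additional safety evaluation. It is not the primary safety or efficacy outcome, and no stated stopping rule uses it.

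**What to change.** In Treatment safety, define the numerator as distinct bloodstream infection episodes, with positive cultures of the same organism inside a stated window counted once. Fix the window before analysis, keep PN follow-up time as the denominator, and report raw culture counts only descriptively.

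Add culture date and organism to the data collection form. Section E itemises biopsies, blood chemistries and feeding history but does not name microbiology, so these fields should not be assumed to be captured.

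If an interval is reported for the rate, base it on between-patient or robust variance. A variance correction alone is not enough, because it would still describe the culture rate.

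The cost is a sentence or two of definition, slightly more chart abstraction, and a lower reported rate wherever repeat positives occurred. Deciding the rule now avoids choosing it after the data are seen.
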